**Study 111-301 Statistical Analysis Plan**

The estimators for each of the analyses are defined in the relevant sections.

Subjects who discontinue from study drug will be encouraged to remain in the study and their non-missing height measurements will continue to be used in calculating the AGV. In the event that missing data does occur despite all efforts, missing standing height will be imputed based on multiple imputation (MI) with pattern-mixture models (Little 1993; Molenberghs and Kenward 2007, pp. 30, 34-37) implemented in PROC MI of SAS where the missing, unobserved observations of the standing height are assumed to follow a missing not at random (MNAR) mechanism. Each imputation will require at least 5 subjects in the same treatment group who also discontinue treatment prematurely at a similar time point (i.e. no more than a 90 day difference between the last dose dates) and have standing height assessments post treatment discontinuation. This is referred to as off-treatment data, and the data for these subjects with standing height assessments post treatment discontinuation will be used as the reference data in the MNAR statement within PROC MI.

PROC MI will be used to impute missing standing height assessments at Week 52. A regression method will be applied with the fully conditional specification (FCS) which can handle both monotone and non-monotone missing standing height data patterns. The baseline covariates for age, strata, height Z-score and AGV and standing height will be included in the VAR statement along with the post-baseline standing height assessments (including off-treatment assessments) at Week 13, 26, 39 and 52. Missing Week 52 standing height assessments will then be imputed from the subjects with reference data (as defined above) using the missing not at random (MNAR) option.

A fixed seed of 5122019 will be specified to ensure reproducibility of the results and the number of imputations set to 10.

In each of the imputed datasets, missing AGV at Week 52 and the corresponding missing change from baseline in AGV will be calculated using the imputed standing height. Note, missing height Z-scores at Week 52 and the corresponding change from baseline will also be calculated. For each subject whose missing Week 52 value is imputed, the 10 imputed values will be provided in a data listing that will be included in the appendix of the CSR.

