**Study 111-301 Statistical Analysis Plan****14.3.3 Sensitivity and Supplementary Analyses Defined for AGV**

The following sensitivity and supplementary analyses are proposed for assessing the robustness of the results of the primary analysis. All visits referred to in the analyses, are based on the analysis windows described in Section 5.4. Summary tables for the models and descriptive summary statistics tables will be provided for each sensitivity analysis.

Sensitivity Analysis: Washout model where missing data for an endpoint for both treatment groups will be imputed using data from the placebo arm.

This approach addresses the same estimand as the primary analysis but with an alternative estimator. Employing this model, any potential BMN 111 treatment effect in those patients in the BMN 111 active group who are off-treatment will be washed out. Specifically, for the washout imputation, the missing data in an endpoint for both treatment groups will be imputed using observed endpoint data from the placebo arm.

PROC MI will be used to impute the missing standing height assessments at Week 52, as described for the primary analysis. However, for this analysis, according to the washout specifications, only placebo data (including off treatment assessments) will be used in the missing not at random (MNAR) option to implement the control-based pattern imputation. Therefore, for the subjects in the BMN 111 active treatment group, no observed post baseline assessments will be considered in the imputation process.

Supplementary Analysis 1: ANCOVA model on completers.

This approach addresses the same estimand as the primary analysis, except that the intercurrent event is defined as subject discontinuation from the study. In this analysis, the estimator will be the difference between the two randomized groups in the mean change from baseline in AGV at Week 52, observed from subjects who have non-missing AGV observation at 52 weeks. The LS means of the change from baseline in AGV at 52 weeks will be estimated for both the randomized groups by applying the ANCOVA model without multiple imputation described in the primary analysis. In this analysis, only subjects with observed AGV change from baseline at 52 weeks will be included. No imputation will be performed for missing 52-week standing height measurements.

Supplementary Analysis 2: ANCOVA model excluding assessments that occur post either limb lengthening or growth hormone/gonadotropin-releasing hormone.

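### Read literally, SAP 14.3.2 fills a leaver's missing Week 13-39 heights under MAR from both arms together and then uses them to predict Week 52, against its own MNAR assumption

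*SAP*

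**What the plan says.** SAP 14.3.2 opens with a general assumption, not limited to any visit: "the missing, unobserved observations of the standing height are assumed to follow a missing not at random (MNAR) mechanism". The operational text that follows is narrower.

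- **Target.** "PROC MI will be used to impute missing standing height assessments at Week 52".
- **Method.** FCS regression, chosen because it handles monotone and non-monotone gaps.
- **Variables.** "The baseline covariates for age, strata, height Z-score and AGV and standing height will be included in the VAR statement". The list also holds the four later heights, Weeks 13 to 52, with values measured off treatment counted in. Treatment group is absent, and neither a BY-treatment statement nor a separate run per arm is mentioned.
- **MNAR step.** "Missing Week 52 standing height assessments will then be imputed from the subjects with reference data (as defined above) using the missing not at random" (the PROC MI feature of that name). No rule is given for missing heights at Weeks 13, 26 or 39.
- **Where treatment enters.** The reference set: "Each imputation will require at least 5 subjects in the same treatment group who also discontinue treatment prematurely at a similar time point", with last doses no more than 90 days apart and heights measured after stopping.
- **Fallback.** With fewer than 5 such subjects, multiple imputation is dropped. Week 52 height is then extrapolated from the child's last height at the child's own baseline AGV.

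Height Z-score (14.4.1) is computed from the same imputed heights, and sitting height (14.4.2) is imputed in the same way. The washout analysis (14.3.3) starts from the same set-up: "PROC MI will be used to impute the missing standing height assessments at Week 52, as described for the primary analysis". It then restricts the MNAR reference to placebo data and says that observed post-baseline heights of BMN 111 children play no part.

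**The concern.** FCS fills every incomplete variable in its list, not only the last one. Suppose a child stops drug and leaves before Week 26. Weeks 26, 39 and 52 are all missing, but the off-treatment rule is attached only to Week 52. With no treatment term and no per-arm run, Weeks 26 and 39 are filled by regression on all children of both arms, most of them still on assigned treatment. The Week 52 draw uses the same-arm off-treatment regression, but its predictors already carry an average of the two arms' growth.

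The imputed value then follows neither the stated MNAR assumption nor a clean MAR one. All three endpoints in the confirmatory sequence use heights imputed this way.

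**Working it through.** **1. The plan's own figure.** Inputs from SAP 4.5: 55 per arm, difference 1.75 cm/yr, SD 2.80, two-sided 0.05. Power is 0.906 (normal) or 0.901 (noncentral t, 108 df), matching the stated 90% or so. The standard error of the difference is 2.80 × √(2/55) = 0.534 cm/yr.

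**2. When the model runs at all.** Five reference subjects are 5/55 = 9.1% of an arm, all stopping drug within 90 days of each other and still being measured.

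**3. Hand check of the worst pattern.** Assume leavers with no post-baseline height and an effect that persists in full after stopping.
- A pooled fill carries half the effect: 1.75/2 = 0.875 cm/yr.
- By Week 39 (0.75 year) a BMN 111 leaver is about 0.875 × 0.75 = 0.66 cm too short and a placebo leaver 0.66 cm too tall.
- At Week 52 the error lies between 0.66 cm (carried over) and 0.875 cm (fully extrapolated).
- With 10% leaving each arm, the bias is between -0.10 × (0.66 + 0.66) = -0.13 and -0.10 × (0.875 + 0.875) = -0.175 cm/yr.

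**4. Simulation.** Assumptions not in the documents: yearly growth SD 1.2 cm given baseline AGV, height measurement SD 0.3 cm, 9% reference subjects per arm stopping at the same time as the leavers, and the effect either fully kept or fully lost on stopping. It uses 150,000 children per arm, so it shows bias and not noise, and one sequential pass with baseline height, baseline AGV and earlier heights as predictors. Bias in the treatment difference, cm/yr:

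| Effect after stopping | Last height | Leavers BMN 111 / placebo | Weeks 13-39 pooled (literal reading) | Weeks 13-39 by arm only | Same-arm off-treatment reference at every visit |
|---|---|---|---|---|---|
| Kept | Day 1 | 10% / 10% | -0.162 | +0.004 | +0.003 |
| Kept | Week 13 | 10% / 10% | -0.060 | +0.002 | +0.001 |
| Kept | Week 26 | 10% / 10% | -0.010 | +0.002 | -0.001 |
| Lost | Day 1 | 10% / 10% | -0.002 | +0.143 | -0.001 |
| Lost | Week 13 | 10% / 10% | +0.030 | +0.083 | +0.001 |
| Lost | Week 26 | 10% / 10% | +0.022 | +0.032 | +0.001 |
| Lost | Day 1 | 10% / 0% | +0.069 | +0.147 | -0.003 |
| Lost | Day 1 | 0% / 10% | -0.079 | 0.000 | -0.002 |

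The first row falls inside the hand-check range. At 20% leaving each arm in that pattern, the bias was -0.323. For leavers last seen at Week 26, it was at most 0.05 in absolute size in every case run.

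**5. Second set of runs.** With 10% leaving per arm, or 4% of placebo and 15% of BMN 111, leavers' heights were off by about 0.2 to 0.9 cm in nearly all runs. The bias in the difference ran from about -0.16 to +0.05 cm/yr. The same-arm reference at every post-stop visit stayed within about 0.002.

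**6. Cycling.** With 55 per arm, leavers at Week 16, 14 reference subjects per arm and the effect lost, full FCS cycling gave a median bias of about -0.05 cm/yr. A single pass gave about -0.01 to +0.01.

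**7. Scale.** A bias of -0.16 is 0.16/0.534 = 0.30 standard errors and 0.16/1.75 = 9% of the design difference. Design power would fall from 0.906 to Φ(1.59/0.534 - 1.96) = 0.85. A bias of +0.05 is 0.09 standard errors.

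**The case against.** The strongest reply is that SAP 14.3.2 nowhere says the earlier visits are filled under MAR or from pooled arms. It assumes MNAR for missing height generally, requires same-arm references, and does not exclude a per-arm run. On that view only a clarification is missing. This stands in part, because pooling is an inference from the variable list. But the list, algorithm, seed and number of imputations are all fixed, and a program written to that text would pool. A per-arm run would not rescue it either: the by-arm column shows +0.14 cm/yr if the effect is lost, because on-treatment heights still fill visits after stopping.

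Several stronger readings are tempting and should not be adopted.

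- **Treatment plays no part in the imputation.** It does, through the reference set at Week 52, and the endpoint uses only Day 1 and Week 52 heights (14.3.1). Weeks 13-39 act as predictors only.
- **Leavers in the two arms are always pulled together, so the error is conservative.** The sign changes across the cases above.
- **The type I error is compromised.** Nothing here shows that. A run with no treatment effect gave no bias.
- **The washout analysis shares the fault.** SAP 14.3.3 bars observed post-baseline BMN 111 heights, which contradicts arm mixing there. What remains is to make the code honour that statement, since it borrows the primary set-up.

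It is also fair that some illustrations need heavy discontinuation. Fourteen reference subjects plus 2 to 8 leavers is 16 to 22 of 55, or 29% to 40% of an arm.

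**Conclusion.** The point holds as an internal conflict with a modest numerical effect. The stated rule, followed as written, gives an estimator that does not match the stated missing-data assumption, and a better rule is available at little cost.

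With about 10% leaving per arm, the bias is roughly -0.16 to +0.05 cm/yr, or about +0.07 if only the BMN 111 arm loses 10% and the effect is lost. It is unlikely to decide a trial designed around 1.75 cm/yr. It arises only if at least 5 same-arm reference subjects exist and the leaver also misses one or more of Weeks 13-39. The figures rest on assumed leaver rates, growth variability and persistence of effect, none of which the documents give. They illustrate size and do not predict it.

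**What to change.** Amend SAP 14.3.2 as follows.

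- For children who stopped drug, impute missing heights in visit order. Use the same-arm off-treatment reference in the MNAR statement at every missing visit after discontinuation, not only Week 52.
- Fill intermittent on-treatment gaps within arm.
- Apply the same rule to sitting height (14.4.2).
- In the washout model (14.3.3), use the placebo reference at every missing visit, so that the code agrees with the statement that no observed post-baseline BMN 111 heights are used.

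The cost is a few sentences and a few lines of PROC MI code. The drawback is that reference subjects must have a height at each visit concerned, so the minimum of 5 has to be checked visit by visit and the fallback may apply more often. The near-zero bias shown for this option is a large-sample result. Five reference subjects cannot support a regression on about 10 predictors (age, three stratum terms, Z-score, AGV, baseline height and three earlier heights), so the amendment should also say how the predictor list is shortened when the reference set is small.

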Subjects who discontinue from the study drug will be encouraged to remain in the study and their non-missing height measurements will continue to be used in calculating the AGV and to be included in the analysis per intend to treat principle. In the event that missing data does occur despite all efforts, missing standing height will be imputed based on multiple imputation (MI) with pattern-mixture models (Little 1993; Molenberghs 2007) implemented in Proc MI of SAS where the missing, unobserved observations of the standing height are assumed to follow missing not at random (MNAR) mechanism. Each imputation will require sufficient standing height data collected from the subjects in the same randomization group who also discontinue treatment prematurely (but remain in the study), referred to as off-treatment data, as these subjects will be used as the reference data for MI. Ten (10) sets of imputations of the missing standing heights will be constructed from MI and the AGV at the missing time points will be calculated based on these 10 sets of data. For

	Study 111-301 Amendment 4	Page 105
---	---------------------------	----------

each subject whose value is imputed, the 10 imputed values will be provided in a data listing that will be included in the appendix of the CSR. The above-mentioned Mixed model will be applied to the 10 imputed data sets from MI. The analysis results based on the 10 imputed datasets will be summarized using Proc MIANALIZE in SAS.

In the event there is insufficient data to perform the imputations for subjects who discontinue the treatment early, then the mixed model will be applied without multiple imputations. The study is considered positive if the primary test is significant in favor of BMN 111.

The AGV and its change from baseline at each scheduled post-treatment visit will be summarized at Week 26 and Week 52 using descriptive statistics (mean, SD, median, Q1, Q3, minimum, and maximum) per group.

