Each of the 10 imputed datasets will be analyzed using an ANCOVA model that includes the following fixed-effect terms:

- Treatment group
- Stratum (Male Tanner Stage I, Female Tanner Stage I, Male Tanner Stage >I, Female Tanner Stage >I)

Study 111-301 Statistical Analysis Plan

- Baseline age
- Baseline AGV
- Baseline height Z-score

SAS PROC MIXED will be used to perform the analysis.

PROC MIXED;

CLASS Stratum Treatment;

MODEL Change from baseline in AGV at Week 52 = Baseline_Age Baseline_AGV
Baseline_Height_Z-Score Treatment Stratum;

LSMEANS Treatment / DIFF = control (“Placebo”) CL;

RUN;

For each imputed dataset, PROC MIXED will generate the least-squares (LS) mean change from baseline in AGV at Week 52 for each treatment group, along with the difference in LS means (calculated as BMN 111 – Placebo). PROC MIANALYZE will then be used to combine all of the estimates across the 10 imputed datasets in order to generate an overall estimate for each treatment group, and for the difference between treatment groups, with a 95% confidence interval for the difference and 2-sided p-value. The study will be considered positive if the 2-sided p-value in favor of BMN 111 is <0.05.

If there are less than 5 subjects with reference data as defined above then missing standing height at Week 52 (i.e. Day 365) will be imputed by applying the baseline AGV (cm/yr) to the last available height assessment as follows:

Standing Height at Day 365 =

$$\text{Last Assessed Height} + \frac{\text{AGV at Baseline}}{365.25} \times (365 - \text{Study Day of Last Height Assessment})$$

Based on this imputed standing height, the height z-score and AGV at Week 52 will be calculated. The ANCOVA model will then be applied to AGV at Week 52.

In the event that there are no subjects who discontinue treatment early with a missing assessment at Week 52 the ANCOVA model will be applied without any imputation.

This ANCOVA model analysis without imputation will be repeated on the PP population.

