14.4.1 Height Z-Score

Standing height is measured at Screening, Day 1, Week 13, Week 26, Week 39, and Week 52. Each measurement of standing height will be converted to an age-and sex-appropriate standard deviation score (SDS), also referred to as a Z-score, by comparison with reference data available for average stature children from the Centers for Disease Control and Prevention (CDC).

The following key secondary hypothesis will be tested (two-tailed):

H₀: Difference in mean height Z-score change from baseline at week 52 between BMN 111 group and the placebo group = 0

H_a: Difference in mean height Z-score change from baseline at week 52 between BMN 111 group and the placebo group ≠ 0

Height Z-score will be analyzed using the same methods and estimand formulation as the primary analysis. If multiple imputation is applied for testing the primary endpoint then the null hypothesis of no difference between the BMN 111 group and the placebo group in the mean change from baseline in the height Z-score at the Week 52 time point will also be tested based on 10 imputed data sets. Missing height Z-score at Week 52 will be calculated from the imputed standing height at this visit, as described for the primary endpoint. If multiple imputation is not applied for the primary endpoint, then the Week 52 height Z-score will be imputed as described above in Section 14.3.2.

SAS PROC MIXED will be used to test the null hypothesis using an ANCOVA model described below.

Study 111-301 Statistical Analysis Plan

PROC MIXED;

CLASS Stratum Treatment;

MODEL Change from baseline in Height Z-score at Week 52 = Baseline_Age
Baseline_AGV Baseline_Height_Z-score Treatment Stratum;

LSMEANS Treatment / DIFF= control (“Placebo”) CL;

RUN;

The least-squares (LS) mean change from baseline in height Z-score at Week 52 will be presented for each treatment group, along with the difference in LS means (calculated as BMN 111 – Placebo), the 95% confidence interval for the difference, and 2-sided p-value. In the event that the primary endpoint test is positive, the testing on the key secondary is considered to be confirmatory. The endpoint is considered positive if the 2-sided p-value in favor of BMN 111 is < 0.05.

This analysis will be repeated on the PP population, using the same approach as described for the primary endpoint. In addition, the sensitivity and supplementary analyses of height Z-score [described in section 14.3.3] will be performed using the FAS population.

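### If multiple imputation is triggered, ten imputations leave avoidable Monte Carlo error in the three gated tests; 100 or more would remove most of it

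*SAP*

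**What the plan says.** SAP 14.3.2 fixes both the seed and the number of imputations: "A fixed seed of 5122019 will be specified to ensure reproducibility of the results and the number of imputations set to 10". Protocol 14.2.1 agrees on the number: "Ten (10) sets of imputations of the missing standing heights will be constructed from MI". The ten analyses are pooled with PROC MIANALYZE, and the decision rule is: "The study will be considered positive if the 2-sided p-value in favor of BMN 111 is <0.05".

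The number carries through the hierarchy. SAP 14.4.1 says that height Z-score "will also be tested based on 10 imputed data sets" if multiple imputation is used for the primary endpoint, and SAP 14.4.2 does the same for the upper to lower body segment ratio. SAP 14.2 tests the three endpoints in series, each at 0.05.

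Multiple imputation is conditional. "Each imputation will require at least 5 subjects in the same treatment group who also discontinue treatment prematurely at a similar time point", which the SAP defines as "no more than a 90 day difference between the last dose dates", and those children must have heights measured after stopping. "If there are less than 5 subjects with reference data as defined above then missing standing height at Week 52" is instead projected from the child's baseline growth velocity, with no random draw. If no child who stopped treatment early lacks a Week 52 value, nothing is imputed.

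Neither document justifies ten, states an expected missing-data rate, limits Monte Carlo error, or says how to treat a p-value close to 0.05.

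**The concern.** The pooled estimate from M imputations has a random component that depends only on the seed. Its standard deviation is sqrt(B/M), where B is the between-imputation variance. Fixing the seed records one draw of that component and does not shrink it. B is larger when few reference children inform the imputation, and the SAP allows as few as five.

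If a p-value lands close to 0.05, the pass or fail at that gate could reflect the draw rather than the data. A failure at one gate also removes confirmatory status from every later test. The noise can be reduced at almost no cost, and the plan leaves it in.

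**Working it through.** **1. The plan's own figure.** Inputs from SAP 4.5: 55 per arm, difference 1.75 cm/year, SD 2.80, two-sided 0.05.
- SE = 2.80 × sqrt(2/55) = 0.534, so t = 1.75/0.534 = 3.28 and p = 0.0014 on 108 df.
- Power by the noncentral t is 90.1%, so the stated 90% is reproduced. The documents give no Monte Carlo figure to reproduce.

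**2. Formula.** With T the total variance of the pooled estimate, Monte Carlo SD/SE = sqrt((B/T)/M). For a limiting (infinite-M) p of 0.05, 95% of seeds give z between 1.96 − 1.96·s and 1.96 + 1.96·s, where s is that ratio.

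**3. Numbers.** The share B/T is an assumption.

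| B/T | M | s | z range | p range |
|---|---|---|---|---|
| 5% | 10 | 0.071 | 1.821-2.099 | 0.036-0.069 |
| 5% | 100 | 0.022 | 1.916-2.004 | 0.045-0.055 |
| 11.6% | 10 | 0.108 | 1.749-2.171 | 0.030-0.080 |
| 11.6% | 100 | 0.034 | 1.893-2.027 | 0.043-0.058 |
| 11.6% | 200 | 0.024 | 1.913-2.007 | 0.045-0.056 |

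At a limiting p of 0.04 and a share of 11.6%, about 19% of seeds give p ≥ 0.05 with M = 10, and about 0.3% with M = 100.

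**4. Where the assumed shares come from.** The 11.6% is the median (range 8% to 18%) in a simulation with 5 of 55 children imputed per arm from 14 same-arm reference children. That scenario is itself an assumption and a heavy one: it means 19/55 = 35% stopping treatment in each arm.

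A second simulation drew from 5 or 10 reference children per arm, with 55 per arm, SD 2.80, an unadjusted comparison and at most one covariate. At a limiting p of 0.05 it gave:

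| Missing per arm | References per arm | M | 95% range of p |
|---|---|---|---|
| 1 | 10 | 10 | 0.042-0.061 |
| 1 | 5 | 10 | 0.036-0.079 |
| 3 | 10 | 10 | 0.036-0.072 |
| 3 | 10 | 200 | 0.047-0.054 |
| 6 | 10 | 10 | 0.030-0.090 |
| 6 | 10 | 200 | 0.044-0.057 |
| 3 | 5 | 10 | 0.025-0.127 |
| 3 | 5 | 200 | 0.040-0.072 |

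With 10 references, the median fraction of missing information (close to B/T) was 4.4% for 3 missing and 10.2% for 6 missing, which is in line with the 5% to 12% used above.

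**5. Away from the gate.** At a limiting p of 0.001, at least 98.9% of seeds stayed below 0.05 in every simulated scenario. Averaged over sampling variation at the planned effect with s = 0.108, the M = 10 decision differs from the infinite-M decision in about 1.4% of trials. With s = 0.034 (M = 100) the figure is about 0.5%. Both are conditional on multiple imputation being used.

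**The case against.** The strongest reply is that the branch may never run. Five qualifying off-treatment children are 5/55 = 9% of an arm, and Protocol 9.3.4 makes retention a priority. With fewer, or with no early discontinuer missing Week 52, the gated tests involve no seed. This stands, and it makes the point conditional. It does not remove it, because multiple imputation is the SAP's first-choice method.

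Second, near the planned effect the decision rarely depends on the seed. That also stands for growth velocity. The documents give no power calculation for height Z-score or segment ratio, so a borderline value at the second or third gate cannot be excluded.

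Third, a reader might infer that the sponsor could pick a favourable seed, or that type I error is inflated. The documents do not support either. Seed and number are fixed in advance, and the standard pooling variance, W + (1 + 1/M)B with W the within-imputation variance, already charges for finite M. Type I error was not simulated.

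Fourth, a larger M does not help most where the problem is worst. With 5 references and 3 missing per arm, p still ranges over 0.040-0.072 at M = 200. The Week 52 imputation model has about 11 coefficients: "The baseline covariates for age, strata, height Z-score and AGV and standing height will be included in the VAR statement", together with the later heights. Five children cannot support that. This is correct, and it is a separate weakness.

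**Conclusion.** The point holds as a conditional, low-severity improvement. Where multiple imputation is triggered, ten imputations leave a Monte Carlo SD of about 7% to 11% of the standard error, if between-imputation variance is 5% to 12% of the total. The shares are assumptions, because the documents state no missing-data or discontinuation rate; very small reference sets would give larger shares. The simulations used unadjusted growth-velocity comparisons with equal missingness in both arms, and the key secondary endpoints were not simulated separately.

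A reader might go further and conclude that the primary result would hinge on the seed in general. That does not follow: only a result near 0.05 in the multiple-imputation branch is affected. The washout and subgroup analyses carry no confirmatory gate and were not simulated, so no instability is claimed for them.

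**What to change.** Before unblinding, replace 10 with at least 100 imputations, preferably 200, keeping the seed, wherever the number appears in SAP 14.3.2, 14.4.1 and 14.4.2. Report the Monte Carlo error of each pooled estimate, sqrt(B/M), and of each p-value. Use the same number in the washout and subgroup analyses for consistency only.

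The cost is a little computing time and edits in three SAP sections. The listing of each child's ten imputed values, promised in SAP 14.3.2 for the CSR appendix, would become the first ten draws or the mean and range. The protocol synopsis and sections 14.2.1 and 14.2.2 also say ten, but Protocol 14.8 lets the SAP prevail without an amendment.

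The five-child reference minimum and the size of the imputation model should be reconsidered separately, since more imputations do not resolve them.
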